Exploratory outcomes will include change in anxiety and depression, as measured by the Hospital Anxiety and Depression Scale (HADS)³, cognition as measured by the Montreal Cognitive Assessment⁴ and measures of attention such as the Symbol Digit Modalities Test (SDMT) and the Digit Span Test (DST)³. Additionally, we will assess change in group cohesion or camaraderie using the Physical Activity Group Environment Questionnaire (PAGEQ). Finally, we will offer instrumented gait analysis to all participants at baseline, 6 months, and 12 months, however this component is optional for participants.

I.b. Background

Parkinson’s Disease, the second most common neurodegenerative condition⁵ presents a significant health concern and the progressive, incurable course of the disease impacts functional abilities of the patient and quality of life for both the patient and caregivers. Exercise is an established supplement to pharmacologic PD treatment and various modalities have demonstrated benefits in gait, balance, PD symptoms, and quality of life measurements.^{6,7,8} Research has encompassed many forms of exercise, including aerobic activities and mindfulness-based practices. Vigorous, aerobic activity has been repeatedly shown to have disease-modifying effects ranging from quality of life to overall cognitive and physical improvement.⁸ Mindfulness-based practices, such as tai chi, have seen a recent surge in interest and an overall beneficial effect for participants.^{9,10} A notable trial compared resistance training, stretching and tai chi interventions among Parkinson’s patients and while both the resistance and tai chi arms showed improvements on multiple measures of physical ability, tai chi demonstrated a significantly greater impact in measures of balance and postural stability.¹¹ Furthermore, resistance training and tai chi were both correlated with improved patient-reported outcomes and participants in the tai chi group who reported benefits were more likely to continue their exercise programs.¹²

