This is a randomized, single-blinded, crossover-controlled, one-year study of non-contact karate for early- to middle-stage PD. The karate classes are developed for and will include only people with PD. Eligible subjects will attend a baseline study visit at Rush University Medical Center. At that time, the study logistics will be reviewed, informed consent process will occur, and each subject will complete brief, individual pre-intervention assessments including a demographic and medical history questionnaire, followed by assessments of overall mobility, gait, and balance (instrumented Timed up and Go, I-TUG; instrumented 2-minute walk, I-WALK, and instrumented sway test, I-SWAY), PD-specific clinical characteristics (Movement Disorders Society Unified Parkinson's Disease Rating Scale, MDS-UPDRS), overall cognition (Montreal Cognitive Assessment, MoCA), executive function and attention (digit span test, DST, and symbol digit modality test, SDMT), anxiety and depression (Hospital Anxiety and Depression Scale, HADS), physical activity (International Physical Activity Questionnaire, IPAQ) and quality of life (PDQ-8). Instrumented gait analysis will be performed to gather more detailed data on stride length and velocity, number of steps to turn, turn duration, and postural sway.¹⁶

During recruitment, and confirmed by the Research Coordinator during the baseline visit, each subject will be asked to identify their preference for karate studio (dojo) location: Roscoe Village, Evanston, Glenview, Park Ridge, or Wilmette.

Once all subjects have completed the objective and subjective baseline assessments, the baseline visit will continue with a one-time, in-person, group training highlighting current research on the benefits of exercise for PD. This training will be delivered by the study team in collaboration with an experienced physical therapist familiar with evidence-based recommendations for safe and effective exercise programs for individuals with early to middle stage PD. Participants will leave the training with printed, publicly available materials on exercise for PD as references.

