Our sample size calculation (see table below) is based on the results from the pilot study with the primary outcome being change in TUG. We powered our original study based on existing literature, in which the mean TUG score for individuals with PD is 14.8 seconds with standard deviation of 5.8 seconds, and minimum clinically important difference values for the TUG ranged from 2 seconds to 5 seconds in various studies.^{1,17} However, our pilot cohort had a pre-intervention baseline mean TUG of 9.6 seconds, standard deviation of 2.1. As per the tables below, if our new cohort has a similar baseline mean TUG, we would need 12 individuals in each arm to detect a difference of 2 seconds with 90% power, however this may not be plausible (i.e., 9 seconds may be close to the limit of how quickly anyone can complete the TUG task). If, however, participants have a more modest baseline to start, which may be expected when recruiting more broadly than at a tertiary referral center, we yield the second half of the table below. Here, we are extrapolating a baseline mean TUG of 12.5 with SD 4.0 (between our pilot data and the existing literature); with 19 individuals per arm, we would be 90% powered to detect a 3s difference between pre- and post-intervention TUG.

If we assume up to 25% attrition in this group of older adults with a chronic neurodegenerative disease, particularly in a longitudinal study over six months, we need to enroll 52 individuals (26 per arm) to yield a total of 40 completing the study.

Baseline mean TUG	Baseline SD TUG	Minimum clinically Important difference	Power	Sample size per arm
9.6	2.1	2s	.9	12
			.8	9
9.6	2.1	3s	.9	6
			.8	4
9.6	2.1	4s	.9	3
			.8	3
9.6	2.1	5s	.9	2
			.8	2
12.5	4.0	2s	.9	43
			.8	32

12.5	4.0	3s	.9	19
			.8	14
12.5	4.0	4s	.9	11
			.8	8
12.5	4.0	5s	.9	7
			.8	6

II.b. Gender of Subjects

There will be no exclusion of subjects based on gender.

II.c. Age of Subjects

Subjects will be 30-90 years of age.

II.d. Racial and Ethnic Origin

There will be no exclusion of subjects based on racial or ethnic characteristics. However, subjects must be fluent in English to participate in the karate classes, as that is the language of instruction, and due to the general lack of appropriately translated neurological and neuropsychological assessments and appropriate normative comparison samples. These factors are critical for accurate administration, scoring, and interpretation of neurological and neuropsychological test data.

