Subjects will then meet with a study team member to complete the TUG (see description below) . Subjects will meet with another study team member to complete the MoCA, DST, and SDMT (cognitive testing). Next, the subject will meet with the PI or another study team member in a private room for the motor portion of the MDS-UPDRS to test bradykinesia, tremor, rigidity, and postural stability.

Subjects will then proceed with the instrumented gait, functional mobility and balance analysis. The use of body wearable inertial motion sensors is a relatively new paradigm in gait, functional mobility and balance analysis. These portable systems allow less costly, less time consuming and noninvasive testing in natural environments compared to traditional marker based approaches (which are conducted in gait laboratories). Gait and functional mobility variables including sit to stand and turn to sit measures using this technology correlate highly with those obtained from traditional optical marker based motion analysis and forceplate approaches.

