The instrumented SWAY (i-SWAY) using one Opal APDM sensor described above will be used to assess balance and postural sway. Subjects will be asked to stand still with their hands across their chests and their feet positioned a set distance apart (scaled to their height) with the sensor applied to the lumbar trunk recording parameters including mean total sway area, path length, jerk, and sway distance in the mediolateral and anteroposterior directions. Postural sway is assessed in standing under the following conditions for 30 seconds for each trial:

- 1) Eyes open (EO) on a firm support surface with the feet apart
- 2) Eyes closed (EC) on a firm support surface with the feet apart.
- 3) Eyes open (EO) on a foam support surface with the feet apart
- 4) Eyes closed (EC) on a foam support surface with the feet apart

Note that trials 1-4 comprise the modified Clinical test of Sensory Integration and Balance which is widely used clinically to test the sensory systems (vision, proprioception, vestibular) that may be deficient and unable to allow for good postural control in patients with neurological disorders, including PD. The trials will be conducted in a non-random order from 1-4 (in order of greater difficulty). Subjects will be carefully monitored during all trials by the Co-Investigator who is a Physical Therapist and well trained in safe and accurate test administration; she will stand directly next to the subject during the

entire testing protocol. If a subject is not able to complete a trial after an initial demonstration then that trial will be deleted from the protocol. It is anticipated that not all subjects will be able to conduct each trial condition because of their balance deficits and the difficulty of certain trials.

Subjects will perform the 3 m and 7 m i-TUG once, respectively. Subjects will perform the standard 2 minute i-WALK test which will allow us to examine fatigue over time in this longer test and will also allow more accurate calculation of gait variability indices by increasing the number of steps; the subject will walk 25 meters, turn and walk back, and repeat this until 2 minutes has elapsed. Subjects will then complete the i-SWAY as described above. In total, the instrumented gait and balance testing will take approximately 10-15 minutes per subject.

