- *Hoehn and Yahr Scale (HY)*: A system used for describing how Parkinson's symptoms progress and the relative level of disability. There are five stages: Stage 0 – No signs of disease; Stage 1 – Unilateral disease; Stage 1.5 – Unilateral plus axial involvement; Stage 2 – Bilateral disease, without impairment of balance; Stage 2.5 – Mild bilateral disease with recovery on pull test; Stage 3 – Mild to moderate bilateral disease; some postural instability; physically independent; Stage 4 – Severe disability; still able to walk or stand unassisted; Stage 5 – Wheelchair bound or bedridden unless aided.¹⁹
- *Timed Up and Go (TUG)*: A well-validated, brief measure of mobility. Administered by a study team member with a stopwatch who has previously measured out the distance between a standard arm chair and a taped line on the ground 10 feet (3 meters) away, subjects sit in a standard arm chair and are instructed that when the team member says "Go", they should stand up from the chair, walk at their normal pace to the line, turn, walk back to their chair at a normal pace, and sit down again. The study team member will record the TUG results in seconds using a stopwatch. This is a recommended test of balance in PD.²⁰

Instrumented- Timed Up and Go (i-TUG): study team member will follow same procedure as TUG described above. For the first trial, subjects will be instructed to walk 3 meters. During the second trial, the distance between the arm chair and a taped line will be increased to 7 meters.

- *Instrumented- WALK (i-WALK)*: a test to examine fatigue over time and will also allow more accurate calculation of gait variability indices by increasing the number of steps. The subject will walk 25 meters, turn and walk back, and repeat this until 2 minutes has elapsed.
- *Instrumented- SWAY (i-SWAY)*: a test to assess balance and postural sway. Subjects will be asked to stand still with their hands across their chests and their feet positioned a set distance apart (scaled to their height) with the APDM sensor applied to the lumbar trunk recording parameters including mean total sway area, path length, jerk, and sway distance in the mediolateral and anteroposterior directions.

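### The primary TUG is described as one stopwatch-timed 3 m sequence with no planned repeat or averaging, so trial-to-trial error enters the change score at both baseline and month 6; two trials for everyone would reduce it cheaply.

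*Combined protocol and SAP*

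**What the plan says.** Section II.a sizes the trial "with the primary outcome being change in TUG". The TUG entry in the list of assessments in section III describes a single stand, walk, turn, return and sit sequence over 3 m, timed by stopwatch. It gives no number of trials and no rule for combining trials.

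The baseline order is in section III, Pre-Intervention Study Visit: "Subjects will then meet with a study team member to complete the TUG", then cognitive testing, then the MDS-UPDRS motor examination, then the instrumented tests. Within the instrumented tests, "Subjects will perform the 3 m and 7 m i-TUG once, respectively". The i-TUG entry in the list of assessments adds that the "study team member will follow same procedure as TUG described above", with 3 m in its first trial and 7 m in its second.

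Other places read differently. Section I.c lists the baseline "assessments of overall mobility, gait, and balance (instrumented Timed up and Go, I-TUG" and so on, without a separate stopwatch TUG. The i-TUG description in section III places the traditional 3 m TUG directly before the 7 m trial, as if it were the first of the pair. For the six- and twelve-month visits, section I.c lists TUG and instrumented gait analysis as separate items. The exploratory-outcomes paragraph before section I.b offers instrumented gait analysis at baseline, 6 and 12 months but says "this component is optional for participants".

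The analysis text in section III.b names only TUG. It mentions neither an i-TUG time nor averaging.

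**The concern.** A change score from one trial per visit carries the trial-to-trial error of both visits. Averaging two trials at each visit halves that part of the variance, and a TUG trial takes seconds. The precision matters here: the pilot change was 0.6 s, and section II.a itself doubts that a 2 s difference is plausible in a cohort like the pilot's.

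There is also a definitional gap. If the stopwatch TUG and the 3 m i-TUG are separate, participants who accept sensors walk the same 3 m task twice and the second walk has no role in the primary outcome. If they are the same trial, the primary would be collected within a component that participants may decline. The plan should say which applies.

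**Working it through.** **1. The plan's own figure.** Section II.a states 19 per arm: "we would be 90% powered to detect a 3s difference between pre- and post-intervention TUG", "extrapolating a baseline mean TUG of 12.5 with SD 4.0". Alpha and sidedness are not stated; two-sided 0.05 is assumed because it reproduces the table. The paired (one-sample) formula gives n = (4.0 × (1.960 + 1.282) / 3)² = 18.7, so 19. With 25% attrition, 19 / 0.75 = 25.3, so 26. Both figures reproduce. They use a single-visit SD of 4.0 s as if it were the SD of change, and they do not separate measurement error from true variation.

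**2. What averaging removes.** Let σ be the SD of trial-to-trial error within a session, taken as independent between trials and equal at both visits.
- One trial per visit puts 2σ² into the variance of change.
- The mean of two trials per visit puts in 2 × σ²/2 = σ².
- The saving is σ².

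**3. On the plan's SD of 4.0 s.** With baseline-to-month-6 correlation ρ (assumed), the variance of change is 2 × 16 × (1 − ρ), which is 16 at ρ = 0.5 and 9.6 at ρ = 0.7.

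| Assumption on trial error | σ² | Reduction, ρ = 0.5 | Reduction, ρ = 0.7 |
|---|---|---|---|
| σ = 0.4 s | 0.16 | 1.0% | 1.7% |
| σ = 0.8 s | 0.64 | 4.0% | 6.7% |
| reliability 0.95, σ² = 16 × 0.05 | 0.80 | 5.0% | 8.3% |
| reliability 0.90, σ² = 16 × 0.10 | 1.60 | 10.0% | 16.7% |

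The first two rows give the 1 to 7% range and the last two the 5 to 17% range. As a share of 40 completers, 1 to 7% is 0.4 to 2.7 people (40 × 0.010 and 40 × 0.067).

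**4. On the pilot's figures.** The pilot reports 9.6 to 9.0 s, n = 15, p = 0.12. Assuming a paired t-test, t on 14 degrees of freedom is 1.656. The standard error is 0.6 / 1.656 = 0.362, and the SD of change is 0.362 × √15 = 1.40 s, with variance about 1.96. Then 0.16 / 1.96 = 8% and 0.64 / 1.96 = 33%.

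**5. Effect on power.** For a between-arm change-score comparison with 20 completers per arm, a 3 s difference, SD 4.0 s and two-sided 0.05 (normal approximation):
- ρ = 0.5: 66.0% with one trial, 68.2% with two at reliability 0.95, 70.5% with two at reliability 0.90.
- ρ = 0.7: 86.5% with one trial, 89.2% with two at 0.95, 91.8% with two at 0.90.

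The gain is about 2 to 5 percentage points.

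**The case against.** The strongest case against the point is that the plan never says the stopwatch TUG is done only once. The word once in the quoted sentence belongs to the i-TUG, and the single stopwatch trial is inferred from a description of one sequence. This stands. The point therefore rests on there being no planned repeat, trial count or combining rule, and not on an explicit limit to one trial.

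A reader might infer that a second 3 m trial is scheduled for everyone and then discarded. The documents do not support that. The instrumented component is optional, its stated purpose is gait, turning and transition parameters, and sections I.c and III leave open whether its 3 m trial is the TUG itself. The better-supported reading is two separate walks for those who accept sensors, given the baseline order and the separate listing at later visits, but it is not settled.

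A reader might also infer that two candidate primary values invite selective reporting. That is weak. The list of assessments defines the TUG as a stopwatch time, the analysis text names TUG, and instrumented gait analysis sits in the exploratory-outcomes paragraph. The text already points to the stopwatch value, and one sentence would settle it.

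Finally, it can be said that the gain is small beside the basis of the sample size. For a between-arm comparison with the same inputs, 2 × 18.7 = 37.4, so 38 per arm would be needed instead of 19. That is a separate and larger issue. It does not remove the case for a nearly free gain in precision.

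**Conclusion.** The concern holds in a limited form. The primary outcome, as described, has no planned repeat, so avoidable trial-to-trial error enters the change score at both visits, and the relation between the TUG and the 3 m i-TUG is not stated.

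The size is uncertain because the documents give no TUG reliability. On the plan's SD of 4.0 s and an assumed correlation of 0.5 to 0.7, the variance of change would fall by roughly 1 to 7% (error SD 0.4 to 0.8 s) or 5 to 17% (reliability 0.90 to 0.95).

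It is tempting to claim 8 to 33%, or 3 to 13 of 40 completers. That requires the SD of change from a 10-week pilot of 15 people to apply to a six-month trial sized on a larger SD. At the upper end it also requires trial error to make up 2 × 0.64 / 1.96 = 65% of the pilot's change variance, and nothing in the documents shows this.

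The case for change rests on a modest expected gain at very low cost, together with a clearer definition of the primary outcome.

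**What to change.** At baseline and month 6, have every participant do two consecutive stopwatch-timed 3 m TUG trials without sensors, in the same order and under the same conditions in both arms. Define the primary outcome as change in the mean of the two. State that the 3 m and 7 m i-TUG values are secondary and never substitute for the primary.

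Averaging the existing TUG with the 3 m i-TUG would be a poorer choice. The i-TUG comes after cognitive testing and the MDS-UPDRS, is done with sensors on, and only some participants will accept it, so measurement conditions would differ between people and possibly between arms.

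The cost is under a minute per visit, one more CRF field, and a possible small practice effect common to both arms. The current text already covers Covid-19 procedures for the remaining 12-month assessments. If the earlier visits are complete, what can still be done is to state, before analysis, how many stopwatch trials were taken, whether the 3 m i-TUG was a separate trial, and which value is primary at both visits.

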
Based on these promising results from the pilot, we are therefore proposing the next step in this line of research, namely, a randomized, controlled trial of a structured karate intervention for individuals with PD. Individuals will receive a one-time, in-person training in best practices for exercise in PD. Due to both the capacity of the karate classes and the scientific approach to detecting changes in PD, subjects will be randomly assigned into either **Arm 1**: immediate participation in the karate class or **Arm 2**: participation in usual exercise for six months followed by karate classes for six months. For participants in **Arm 1**, following the first six months of classes, subjects may choose to continue their participation in karate and in the study, though this will require paying membership fees at the *dojo* (karate studio). For participants in **Arm 2**, following the first six months of usual exercise, participants will then begin 6 months of twice-weekly classes. We will conduct in-person assessments of motor function, attention, and cognition at baseline, six months, and twelve months. We will conduct online assessments of adherence to exercise program, quality of life, anxiety, depression, global impression of change, and group cohesion via bimonthly online surveys. We will assess feasibility with measurement of attendance at each class, and sustainability with the rate of attendance among the participants beyond their first six months of classes.

We hypothesize: 1) Subjects will show improved mobility after 6-months of twice weekly karate classes, as measured by change in Timed Up & Go (TUG)¹ and MDS-UPDRS motor subscore; 2) The majority of subjects will report a positive change from baseline in their overall wellbeing, as measured by a response of “very much improved”, “much improved” or “minimally improved” on the Patient Global Impression of Change Scale (PGIC)² following 6 months of classes; 3) Feasibility will be high, as measured by $\geq 75\%$ attendance rate and a response of “yes” to either “Would you recommend this program to someone else with PD?” or “If available, would you continue to participate in this or a similar karate class?”

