After six months, participants in both arms will have a second in-person study visit in which the pre-intervention assessments will be re-administered (MDS-UPDRS, TUG, IPAQ, MoCA, PDQ-8, HADS, SDMT, DST, and instrumented gait analysis), along with the PAGEQ and PGIC. The PI and co-investigators performing the MDS-UPDRS will be blinded to subjects' assignments. Following completion of all assessments, without the blinded raters present, all participants will be reminded to continue completing the bimonthly online surveys over the upcoming six months, and the Research Coordinator will explain to Arm 2 on the crossing over process into the active intervention (karate classes), and participants will be provided with information on the timing and location of classes. Individuals in Arm 1 will be asked to stay and participate in a brief focus group on the first six months of classes; PI and co-investigators will not be present during the focus group in order to preserve the blind. Subjects will be prompted to share their thoughts on how the intervention impacted their overall wellbeing, balance, and mindfulness; whether the intervention achieved their expectations; whether they intend to continue, and what feedback they would like to provide.

After twelve months, participants in both arms will have a third in-person study visit* in which the pre-intervention assessments will be re-administered (medication regimen, MDS-UPDRS, TUG, IPAQ, MoCA, PDQ-8, HADS, SDMT, DST, and instrumented gait analysis), along with the PAGEQ and PGIC. The PI and co-investigators performing the MDS-UPDRS will remain blinded to subjects' assignments. Following completion of all assessments, all subjects will be asked to stay and participate in a brief focus group to reflect on the entire study. Given the number of subjects, study staff may divide the group into Arm 1 and Arm 2 participants, with concurrently running focus groups in separate rooms to ensure all participants have the opportunity to speak; again, PI and co-investigators performing ratings will not be present to preserve blinding. The script for both groups will be identical.

*Covid-19 Procedures for 12 month study visits:

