Following six months of classes for Arm 1, and six months of usual exercise for Arm 2, the study team will contact subjects to schedule a six-month study visit, consisting of a repeated TUG, HADS, PDQ-8, SDMT, DST, MoCa, medication regimen and falls questionnaire, PAGEQ, PGIC, and MDS-UPDRS

examination. Each subject in Arm 1 will receive their initial response to the “What do you hope to achieve in this class?” prompt, and will be asked to reflect in a written, open-ended manner on whether they feel that they achieved their goal. Individuals in Arm 1 will be reminded that they may continue to attend karate classes, but the usual class fee per the dojo will no longer be waived. Individuals in Arm 2 will be informed that they may now begin karate classes at their dojo of choice for the following six months. This 6-month study visit is different than the 6-month follow-up call that was part of the initial KICK OUT PD pilot study; this six-month study visit is conducted in person, not by phone, and involves retesting of all of the measures from the initial, baseline visit. There will not be a 6-month follow up call in the new KICK OUT 2.

Twelve-month study visit

Following twelve months of classes for those individuals in Arm 1 opting to continue, and six months of classes for participants in Arm 2, the study team will contact subjects to schedule a twelve-month study visit, consisting of a repeated TUG, HADS, PDQ-8, SDMT, DST, MoCa medication regimen and falls questionnaire, PAGEQ, PGIC, and MDS-UPDRS examination. Each subject will receive their initial response to the “What do you hope to achieve in this class?” prompt, and will be asked to reflect in a written, open-ended manner on whether they feel that they achieved their goal. In addition, subjects will indicate their response to the following questions regarding feasibility: “Would you recommend this program to someone else with PD?” and “If available, would you continue to participate in this or a similar karate class?” Following completion of all assessments, all subjects will be asked to stay and participate in a brief focus group to reflect on the entire study. Given the number of subjects, study staff may divide the group into Arm 1 and Arm 2 participants, with concurrently running focus groups in separate rooms to ensure all participants have the opportunity to speak. The script for both groups will be identical.

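### The two yes/no feasibility questions are asked only at month 12, so Arm 1's answers do not match its months 0–6 attendance and mix feasibility with sustainability

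*Combined protocol and SAP*

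**What the plan says.** The third hypothesis, in the aims before section I.b, begins "Feasibility will be high, as measured by". It then names two components: attendance of at least 75%, and a yes to either of two questions. One is "Would you recommend this program to someone else with PD"; the other asks about carrying on with this or a similar class. No time point is given.

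The questions appear in one place, section III, Twelve-month study visit: "In addition, subjects will indicate their response to the following questions regarding feasibility". The Six-month study visit text lists its content as "consisting of a repeated TUG, HADS, PDQ-8, SDMT, DST, MoCa, medication regimen and falls questionnaire, PAGEQ, PGIC, and MDS-UPDRS", plus a written reflection on personal goals for Arm 1, and does not include the two questions. Nor does the bimonthly survey as described in I.c and III.

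The arms reach month 12 in different positions. The visit takes place "Following twelve months of classes for those individuals in Arm 1 opting to continue, and six months of classes for participants in Arm 2". After month 6, Arm 1 "subjects may choose to continue their participation in karate and in the study, though this will require paying membership fees at the" dojo (aims; see also V.f).

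At month 6, Arm 1 attends a focus group that asks, among other things, "whether they intend to continue, and what feedback they would like to provide" (I.c). Section III.b plans descriptive statistics for continued interest and recommendation, and reports attendance for each arm over its active period.

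**The concern.** The two components of one criterion cover different periods in Arm 1. Attendance describes months 0–6, while the yes/no answers come at month 12.

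In between, Arm 1 members have had to choose between paying for classes and stopping. A question about continuing then means something different from the same question put to Arm 2, whose classes have just ended. The aims treat sustainability separately, as attendance beyond the first six months of classes. For Arm 1, the month-12 answers carry some of that second concept into the first.

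Arm 1 members lost between months 6 and 12 would leave no answer, even if they completed all their study classes. Section III.b states no denominator and no rule for non-response, so a high percentage among those who answer could be read as a percentage of everyone assigned.

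**Working it through.** **Timing, from the passages side by side**

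| | Arm 1 | Arm 2 |
|---|---|---|
| Study classes | months 0–6 | months 6–12 |
| Attendance used for hypothesis 3 | months 0–6 | months 6–12 |
| Two questions asked | month 12 | month 12 |
| Gap from end of study classes to questions | 6 months | about 0 |
| Pay-or-stop decision already made? | yes | no |

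The gap in Arm 1 is a gap from the fee-waived classes. Members who pay and continue may still be in class at month 12.

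**The plan's own figures (II.a)**

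- Inputs: 19 per arm after attrition, up to 25% attrition described over six months, 26 per arm, 52 in total, 40 completing.
- Inflation: 19 / (1 − 0.25) = 25.3, rounded up to 26 per arm; 2 × 26 = 52. This reproduces the plan.
- Completers: 52 × 0.75 = 39, against 40 stated. This agrees if each arm's 26 × 0.75 = 19.5 is rounded up to 20.
- II.a gives no sample size or precision for the two questions, and no separate loss figure for months 6–12.

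**Worst-case bound for Arm 1**

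Suppose every responder says yes and every non-responder would say no. The share of those assigned who say yes is then responders / 26.

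- 25% loss in all: 19.5 responders, so 19/26 = 73% or 20/26 = 77%.
- 25% loss by month 6 and none afterwards: unchanged at 73–77%.
- 25% by month 6, then an assumed further 10% of those remaining: 19.5 × 0.90 = 17.6, about 18; 18/26 = 69%.
- 25% by month 6, then an assumed further 25% of those remaining: 19.5 × 0.75 = 14.6, about 15; 15/26 = 58%.
- For contrast, an assumed 10% loss in all: 23 responders; 23/26 = 88%.

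In each case the responders' own figure is 100%.

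**How much of this is due to timing**

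Only losses after month 6 are. In the assumed further-25% case that is about 20 − 15 = 5 people, or 5/26 = 19 percentage points. With no loss after month 6 it is zero. The distance from 100% to 73–77% comes from losses before month 6, which asking earlier would not recover.

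**The case against.** The strongest reply is that little depends on these answers. They are one half of a descriptive criterion. The other half, attendance, is recorded at each class and would show poor uptake in Arm 1 during its active months. Paid attendance after month 6 is also tracked, and is firmer evidence of interest than a hypothetical question. The month-6 focus group adds qualitative information. All of this is right, and it limits how serious the point is. It does not supply the yes/no answer that hypothesis 3 names: the focus group is open discussion, and the written reflection concerns personal goals.

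A reader might infer three stronger things that the documents do not support.

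- **That a comparison of arms is biased.** Section III.b plans no between-arm comparison of these answers. The timing affects how pooled or by-arm percentages are read.
- **That Arm 1 members who stop karate leave the study.** Section I.c says "After twelve months, participants in both arms will have a third in-person study visit", and reminds everyone at month 6 to keep completing the surveys. The aims can be read as making both karate and study participation optional after month 6. That is an ambiguity to reconcile and does not show loss.
- **That late asking inflates the yes rate.** Missing answers from people who lost interest would push it up. A member who stopped, perhaps because of the fee, might say no at month 12 after a yes at month 6, which would push it down. The documents do not settle which dominates.

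**Conclusion.** The point holds as one of unequal timing. Followed as written, the schedule measures one component of hypothesis 3 at the end of study classes in Arm 2 and six months later in Arm 1. Arm 1's answers then do not correspond to its attendance period and overlap with sustainability. The net direction of bias is unknown.

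The bound of 73–77% rests on the protocol's 25% attrition and on counting every non-responder as a no. It is a worst case, not an estimate. The 58% figure adds a second 25% loss in months 6–12 that the documents do not state, and it includes early losses that a change of timing cannot recover. It should not be quoted as an expected result.

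The effect is on the interpretation of hypothesis 3. The TUG outcome and the sample size of 52 are untouched.

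**What to change.** - Ask Arm 1 both questions as written, individual items at the existing six-month visit, and Arm 2 at month 12. Use these end-of-active-period answers for hypothesis 3 and state that time point in the hypothesis.
- Report each question separately, with all assigned participants as the denominator and non-responders shown.
- Report Arm 1's month-12 answers separately, as sustainability.
- Reconcile the aims with I.c on whether Arm 1 members who stop karate remain in follow-up.

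The cost is two extra items at a visit that is already scheduled, and a short amendment. The sample size does not change.

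The six-month visits may already be complete. This is an inference from the Covid-19 text, which deals only with remaining twelve-month assessments, and from the January to June 2019 class dates anticipated for Arm 1. In that case, report the month-12 answers by arm and by Arm 1 continuation status, show non-responders, and do not pool the arms. That needs only a change to the reporting plan.
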